**Clinical** providers may refer interested patients and document their willingness to be contacted by the study through CPRS via their progress notes and using templated language provided to them (See Appendix G). Clinicians may also send referral information via encrypted email with the same templated documentation (or comparable documentation that the Veteran is interested in hearing more about the study and gives permission for research staff to contact them). Following a chart review and preliminary phone screen to determine eligibility, potential participants will be scheduled for an initial telehealth (by video or telephone) appointment during which they will be consented to the study. Consented participants will be instructed to return the informed consent form (ICF) and Authorization for Use and Release of Individually Identifiable Health Information Collected for VHA Research (HIPAA form) to the study team using a prepaid and preaddressed envelope. Once received, a study team member will complete an assessment appointment with the participant via telehealth. After all eligibility criteria are met and the assessment is complete, if telehealth appointments are conducted via VA Video Connect (VVC) platform, participants may receive automated reminders and appointment links over email, consistent with procedures for clinical appointments using VVC. The study statistician will randomly assign eligible participants to one of the two treatment options and will notify the site study coordinator about randomization status. The site study coordinator or other appropriate research team member, will contact the participants to inform them of their group assignment. Those assigned to CABA will be contacted by their therapist and tele-or video-therapy will commence. Those assigned to TAU will be offered a referral for PTSD specialty care. The assessors will be blind to group status throughout the study whenever possible. Consistent with a national VA performance measure that requires 8 sessions to be delivered over a 14 week period, participants will be contacted by phone by a blinded assessor for the mid-treatment assessment 7 weeks after the onset of treatment. Allowing 14 weeks to complete a 10 session treatment protocol accounts for cancellations and missed sessions. Participants will then be seen for follow-up assessments 14 weeks after initiating treatment. In order to minimize drop-out and maximize retention of individuals for intent-to-treat analyses, extensive efforts will be made to stay in contact with all study participants, including individuals who drop out of treatment. CABA participants who are deemed nonresponders or relapsers (do not evidence at least a 20% reduction in PTSD or cognitive symptoms) at the post-assessment or follow-up assessment (or an increase in suicidality or substance abuse), and other participants as clinically appropriate, will be offered alternative treatment or appropriate referrals.

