## 5.5 Study Evaluations

### **Visit schedules**

#### **Pre-enrollment screening:**

- 1) Medical Record Review: Study personnel will review each participant's medical record, including their neuropsychological assessment records, to document severity and type of current cognitive status, medical and psychiatric history, current treatment, and medications.
- 2) Clinical Screening Phone Interview: Study personnel will conduct a brief phone screening to ensure subjects meet initial eligibility criteria. Participants interested in the study will be asked to provide an email address for scheduling video telehealth appointments.

**Study Enrollment:** All eligible participants will complete a consent visit including:

Informed Consent: Study personnel will complete consent procedures. All effort will be made to ensure participants fully comprehend study procedures, risks, and benefits.

**Baseline Assessment:** All eligible participants will complete a baseline assessment visit including:

Baseline Psychological and Cognitive Assessment Battery (see below). This includes assessment of exclusionary diagnoses as well a brief neuropsychological battery, diagnostic interviews, and self-report questionnaires of current emotional and post-concussive symptoms. If an individual is found not be eligible during this assessment, the assessment will be discontinued at that point.

**Treatment Visits:** All eligible patients will be randomized (CABA or TAU). CABA participants will be assigned to a therapist and receive the 10-session intervention (during COVID-19 this will be completed using telehealth modalities); TAU participants will be referred to PTSD specialty care.

**Mid-treatment Assessment:** Participants will complete questionnaires at mid-treatment (approximately 7 weeks after initiation of treatment) designed to assess current emotional and post-concussive symptoms.

**Post-treatment Assessment:** Participants will complete a brief cognitive assessment battery, diagnostic interviews, and questionnaires designed to assess current emotional and post-concussive symptoms (see section B “Data Collection and Assessment” below for a list and description of each battery measure). This will take place approximately 14 weeks after the initiation of treatment.

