#### Cognitive Functioning (all tests were selected because of their excellent validity and reliability, and the availability of large normative databases)

- The Wide Range Achievement Test-4 (WRAT-4) Baseline ability, a NINDS supplemental TBI CDE.
- Hopkins Verbal Memory Test-Revised (HVLT-R) A measure of verbal list learning and delayed recall.
- Wechsler Adult Intelligence Scale-4th Edition, Digit Span Subtest (WAIS-IV) A WAIS-IV subtest that measures attention and working memory, and is a NINDS supplemental TBI CDE.
- Wechsler Adult Intelligence Scale-3rd Edition, Symbol Search Subtest (WAIS-III) WAIS-III subtest measuring processing speed; component of WAIS PSI, a core NINDS TBI CDE. This test will not be administered during telehealth visits.
- Trail Making Test (TMT) DKEFS- trails subtest is a visual-motor task used to measure flexibility in thinking (executive function) and processing speed, a core NINDS TBI CDE. This test will not be administered during telehealth visits.
- Controlled Oral Word Association Test (COWAT) Verbal fluency, a supplemental NINDS TBI CDE.

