For major analyses of central hypotheses (1a-1b and 2a), we propose to use Mixed Effects modeling to account for clustered data (i.e., repeated assessments within individuals, treatment groups, and sites). The mixed effects approach provides more information and more power compared to cross-sectional analyses which focus on analysis of one summary index or time-until event methods and traditional analytic approaches such as a change score, end-point or repeated measures analysis of variance (ANOVA). This method allows inclusion of subjects with missing data or those who were terminated early in the study, without relying on data imputation procedures. Two specific forms of the Mixed effects model strategy are commonly implemented: random regression models, or hierarchical models (HLM) or multilevel models; and mixed model analysis of variance (MMANOVA). Each outcome variable will be graphed versus time for each subject to evaluate what function of time best describes the data. The mixed effects framework is robust with respect to drop-out and missing data, unless the drop-out mechanism or cause of missing is informative. We will use pattern-mixture models to assess if there is bias due to drop out or missing data. As described by Hedeker and Gibbons, these mixed models allow us to assess whether important estimates are dependent on missing data patterns and provide overall estimates of effects by averaging over the various missing-data patterns. In addition, we will consider the extension of the Pattern-Mixture models as described by Guo et al which includes the incorporation of random effects in the Pattern mixture model, allowing subject-to-subject heterogeneity.

Missing data values will be minimized by intensive training of interviewers in techniques of clarifying answers and checking questionnaires while participants are on-site. When missing values are identified, we will employ several approaches. If possible, participants will be rescheduled for missed assessments. Missing data will be examined to assess randomness. The pattern of missing data will be examined according to the procedure recommended by Little and Rubin which includes comparing group differences in the primary outcomes of subjects with versus without missing data. The Mixed effects model allows inclusion of subjects with missing data or those who terminated the study early, without relying on data imputation procedures.

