**Hypothesis 1a)** PTSD symptom severity. Dependent variables: CAPS-V and PCL-5.

**Hypothesis 1b)** Functional impairment. Dependent variables: HVLTR, WAIS-IV (Digit Span subtest), DKEFS (Trails subtest), and COWAT (Verbal Fluency).

Independent variables: Treatment group (2 levels, CABA and TAU), & Time (3 levels, Weeks 0, 7, and 14). Statistical Analysis: We will analyze data on all randomized subjects in whom we have a baseline assessment and at least one post-baseline evaluation by Mixed effects model methods. Preliminary inspection of data will determine whether the outcome is nearly normal, or whether an appropriate transformation is required, or whether a generalized linear mixed model should be considered. The mixed effects model method provides an estimate of the individual variability around the population trend, the variability of the individual intercepts (baseline values) and slopes (changes across time), and the correlation between them. A fully saturated treatment by time model will be utilized for inference. Covariance structure will be chosen based on Akaike's Information Criterion (AIC). Random group level treatment effects will also be evaluated for importance based on the model AIC. This allows for any group level effects to be incorporated into the model. Denominator degrees of freedom will be calculated using the Kenward-Roger small sample correction. The design is a 2 (sites) X 2 (CABA vs TAU) X 3 (baseline, 7, and 14 weeks). The interaction of Site and Treatment X Site will be included and tested as

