"nuisance parameters". However, we do not anticipate any Treatment by Site or Site effects with the balanced design (equal numbers at each site in each group), our standard training procedure of both sites and standard operating procedure used by both sites. In any case, the analysis procedures will include site and site interaction effects to avoid allowing site effects to bias treatment comparisons. If we detect any imbalances between the treatment groups within each site, we will follow the primary analyses above with subsequent analyses considering the imbalances to verify that the conclusions are not affected by imbalances. Analyses will be conducted within and across nested levels of the study design; this will involve within-subject analyses (comparison of occasions of measurement nested within an individual), as well as between-subject analyses (comparison of the CABA and TAU groups, comparison of groups within a site, comparison of sites, etc). Any treatment group comparison can be adjusted for subject-specific characteristics and adjustments for changes in these characteristics over the course of the study can be incorporated into single-subject analyses. All comparisons described in this section can be effectively analyzed using PROC MIXED in SAS statistical software. Based on our ongoing studies, we expect a drop-out rate of <15% after baseline assessment but prior to first post-baseline evaluation. The drop-out rate is taken into account in power analyses, see above.

**Hypothesis 2a)** Patient-centered outcomes. Dependent variables: BDI-II, NSI, and SLS. Independent variables: Treatment group (2 levels, CABA and TAU), and Time (3 levels, Weeks 0,7,14). Statistical Analysis: Data will be analyzed similar to hypotheses 1a and 1b.

**Hypothesis 2b)** Treatment satisfaction. Dependent variables: CSQ. Independent variables: Treatment group (2 levels, CABA and TAU). Statistical Analysis: Hypothesis 2b will be tested using Analysis of Variance, comparing the two groups on the treatment credibility and satisfaction (CSQ).

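### The Hypothesis 1a/1b analysis set removes participants with no assessment after baseline, and for outcomes measured only at weeks 0 and 14 the pattern-mixture check cannot estimate change in drop-outs

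*Combined protocol and SAP*

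**What the plan says.** Section 5.6 of the combined protocol and SAP, under Hypotheses 1a and 1b, analyses "all randomized subjects in whom we have a baseline assessment and at least one post-baseline evaluation". For 1a it names "Dependent variables: CAPS-V and PCL-5", without ranking them. For 1b it names "HVLTR, WAIS-IV (Digit Span subtest), DKEFS (Trails subtest), and COWAT (Verbal Fluency". The model has treatment, three time levels (weeks 0, 7 and 14) and a saturated treatment-by-time structure.

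On attrition, the same section states that "we expect a drop-out rate of <15% after baseline assessment but prior to first post-baseline evaluation". The paragraphs under Outcome analyses say that the mixed model can use the data of people who stop early. They add: "We will use pattern-mixture models to assess if there is bias due to drop out or missing data". They also plan a comparison, following Little and Rubin, of participants with and without missing data. Section 5.1 (Procedures) describes efforts to "maximize retention of individuals for intent-to-treat analyses".

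Table 3, which is headed as updated for telehealth, schedules CAPS-V and the neuropsychological battery at weeks 0 and 14 only. PCL-5, NSI, BDI-II and SLS are scheduled at weeks 0, 7 and 14. Section 5.5 confirms what the week-7 contact contains: "Participants will complete questionnaires at mid-treatment (approximately 7 weeks after initiation of treatment". Of Trails, the list of measures says: "This test will not be administered during telehealth visits".

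**The concern.** Two features combine.

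First, the analysis set discards the people whom the plan expects to lose, although the chosen likelihood method could use their baseline values. If the relation between baseline severity and drop-out differs by arm, the retained participants no longer have comparable baselines. A change-score contrast is then biased.

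Second, four primary dependent variables have a single post-baseline visit. Everyone with a post-baseline value has the same pattern of observed visits (0, 14), so nothing in the data shows how change differs between drop-outs and others. The plan accepts that its mixed model is vulnerable to informative drop-out and offers pattern-mixture modelling as the main answer. For these outcomes that answer needs an assumption that the plan does not supply. Participants and therapists are unblinded, so drop-out that differs by arm is plausible.

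**Working it through.** **Plan's own figure.** The stated N can be reproduced with a week-14 comparison of means, difference 0.5 SD, two-sided alpha .02, 80% power: 2 × (2.326 + 0.842)² / 0.5² = 80.3, so 81 per arm. Then 81 / 0.85 = 95.3, so 96 per arm and 192 in total. At the 15% ceiling, 0.15 × 192 = 28.8, about 29 people, leave the analysis set, and 0.85 × 96 = 81.6 per arm remain.

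**What the pattern-mixture model can estimate.** Count the parameters of a pattern × treatment × time model against those the schedule identifies:
- CAPS-V, HVLT-R, Digit Span, COWAT, participants with a post-baseline value: one pattern (0, 14). All 4 parameters are estimable, but there is no second pattern to compare.
- The same outcomes with baseline-only records kept: patterns (0, 14) and (0). 6 of 8 are estimable. The two missing are the drop-outs' change, one per arm.
- PCL-5, linear time, patterns (0, 7, 14) and (0, 7): 8 of 8 are estimable.
- PCL-5, saturated time, patterns (0, 7, 14), (0, 7) and (0, 14): 14 of 18. A restriction or a trend assumption is needed here too, but week 7 gives some information on change in those who miss week 14.

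**Effect of the exclusion.** With both weeks complete and a saturated model, the treatment-by-time contrast equals the difference in mean change. Suppose a fraction p of one arm is excluded and those people have a baseline d SD above that arm's mean. The retained baseline mean falls by p·d/(1 − p). Their week-14 mean falls by only rho times that (equal SDs), so mean change shifts by (1 − rho)·p·d/(1 − p). Inputs: p = 0.15 (plan's ceiling); d = 0.5 (assumed); rho = 0.45² = 0.2025 (the plan's autoregressive structure over two steps) or 0.45.
- rho = 0.2025: 0.7975 × 0.15 × 0.5 / 0.85 = 0.070 SD.
- rho = 0.45: 0.55 × 0.15 × 0.5 / 0.85 = 0.049 SD.

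**Informative drop-out.** If missing week-14 values in one arm are D SD worse than predicted, bias = p·D (D is assumed):
- D = 0.25: 0.15 × 0.25 = 0.0375 SD, or 7.5% of the 0.5 SD design effect.
- D = 1.0: 0.15 × 1.0 = 0.15 SD, or 30%.
- Same D and same drop-out in both arms: zero.
- Same D, drop-out 20% and 10%: (0.20 − 0.10) × D = 0.025 to 0.10 SD.

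**Large-sample simulation** (assumed true effect −0.50 SD; drop-out about 16% in CABA and 15% in TAU; random in TAU; logistic slope of 1 per SD in CABA; rho from 0.45 down to 0.2025):
- CABA drop-out depends on baseline: the set as written gives −0.42 to −0.39. Keeping baseline-only records gives −0.50.
- CABA drop-out depends on the unseen week-14 score: the set as written gives −0.58 to −0.61. Keeping everyone gives −0.61 to −0.64.

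**Effect on the test.** With 81.6 per arm, a week-14 comparison and no true effect, a bias of 0.05, 0.10 or 0.15 SD moves the rejection rate at alpha .04 to about .050, .082 or .138.

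**The case against.** Several stronger readings are tempting, and the documents do not support them.

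- *The check fails for all primary outcomes.* PCL-5 is a 1a outcome of equal standing with a week-7 visit, so drop-out between weeks 7 and 14 can be examined. Those lost before week 7 are still excluded. Trails is a separate problem: it has no value at telehealth visits, so week-14 imputation is not the remedy.
- *There is no other safeguard.* The Little and Rubin comparison is planned, missed assessments are to be rescheduled, and people who stop treatment or withdraw may still be assessed. These count. For the two-visit outcomes, however, the comparison can show only baseline differences, and only if excluded participants are brought back for it.
- *The set contradicts intention to treat.* It starts from randomised participants and does not select on treatment received. It is a common modified intention-to-treat set. It sits awkwardly with the stated aim and with the plan's remarks on including early leavers, but it is not a flat contradiction.
- *The check must return the completers' estimate.* The plan does not say whether the post-baseline requirement applies per participant or per outcome. Per participant, someone with week-7 questionnaires stays in and contributes a baseline CAPS-V. The result then depends on the restriction chosen. The defect is that none is stated.
- *The biases are expected values.* They use the ceiling and put the whole deviation in one arm. Earlier studies lost 12.3% and 11%. At 12.3% and D = 0.25 the bias is 0.123 × 0.25 = 0.03 SD, about 6% of 0.5 SD.

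Table 3 is also the telehealth schedule. Participants assessed in person may have had a 6-month visit, whose content is not shown. The planned model nevertheless uses only weeks 0, 7 and 14. Finally, no method detects not-at-random drop-out from observed data alone.

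**Conclusion.** The point holds for CAPS-V, HVLT-R, Digit Span and COWAT under the telehealth schedule. It has two parts. The analysis set discards usable baseline data and exposes the contrast to bias when drop-out depends on baseline differently by arm. The pattern-mixture check, without a stated restriction, cannot estimate the drop-outs' change. The identification result follows from the visit schedule and needs no numerical assumption. The sizes are illustrations at the 15% ceiling with one-arm deviations that the documents do not give: 0.05 to 0.07 SD from exclusion, 0.04 to 0.15 SD from informative drop-out. The upper end is large enough to matter for a 0.5 SD effect. The lower end, or balanced drop-out, is minor. This should be corrected before analysis; it does not undermine the trial.

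**What to change.** 1. In section 5.6, under Hypotheses 1a and 1b, define the analysis set as all randomised participants with a baseline value, in the arm assigned, and keep baseline-only records in the likelihood. This removes the bias if drop-out is at random given baseline. It does not cure informative drop-out, as the second simulation scenario shows. It also settles the per-participant or per-outcome ambiguity.

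2. In the missing-data text under Outcome analyses, for CAPS-V, HVLT-R, Digit Span and COWAT, replace the pattern-mixture check with a pre-specified delta-adjusted multiple-imputation analysis. Vary the deltas separately by arm, and fix and justify their range in advance. Describe it as showing how far the conclusion depends on the missing values, not as a test for bias.

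3. Keep pattern-mixture models for PCL-5, BDI-II, NSI and SLS, which have three visits, and state the time trend or restriction used.

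4. Deal with Trails separately, since it is not administered at telehealth visits.

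The cost is SAP wording and a small amount of programming. Visits and sample size do not change.

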**Sample size and power.** Power analyses are performed for primary hypotheses *1a, 1b and 2a*, incorporating the longitudinal nature of the design. We propose a Random Regression model (also known as Multilevel or Growth Curve Models) as a basis of the analysis. In this approach, the repeated measures over time for each individual subject form a trajectory that can be described by a relatively simple model with a few parameters, here a linear model described by intercept (baseline value) and slope (rate of change). With random assignment to groups, there should be no group differences in baseline values, and slopes differences reflect treatment effects. With repeated measures, repeated observations within subjects are potentially correlated, impacting tests of significance. When within subject correlation is properly incorporated, the repeated measures analysis takes full advantage of all information obtained from each subject, thereby greatly increasing statistical power over cross-sectional methods. This approach can model differential patterns over repeated assessments instead of totals at one point and therefore increases the reliability of the measurement of response (since the slope combines repeated measures which cancel much of the error of measurement), and increases the protection against the major effects of missing data (since one can impute from the non-missing data for that subject as well as for other similar subjects). These result in increased power to detect effects and precision of effect size estimation without increased sample size.

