Power calculations can be made for repeated measures designs under specified assumptions. Hedeker et al. extend Diggle et al.'s method for various covariance structures. Procedures described by Hedeker et al. for Random Regression Models were used for the proposed study to estimate needed sample size using RMASS (see Hedeker <http://tigger.uic.edu/~hedeker/ml.html>). Data from our previous studies were used to calculate effect sizes. The design consists of a 2 (sites) X 2 (CABA vs TAU) X 4 (baseline, 7, and 14 weeks) where the slope is the dependent measure. Site and Treatment by Site interaction were included as "nuisance parameters", that is, included to account for possible overall site effects (Site) or possible site differences in treatment effects (Treatments X Site). With a balanced design (equal numbers at each site in each group), ignoring these would not increase the probability of Type I error, but would increase the Error Sum of Squares (SS) and probability of Type II error. The main effect of treatment represents the common effect size across sites if there is one, or the average site effect, if there is heterogeneity across sites. This is true because sample sizes will be balanced across treatment groups and sites. In any case, the analysis procedures will include site and site interaction effects to avoid allowing site effects to bias treatment comparisons. However, if we detect imbalances between the treatment groups within each site, we will follow the primary analyses with subsequent analyses considering the imbalances to verify that conclusions are not affected by imbalances.

Other assumptions needed are number of repeated measures, alpha-level, nature of the hypothesis (one- or two-sided), drop-out rate, and variance-covariance matrix of the longitudinal data. We assume an overall Type-I error levels alpha of .01 to .02, drop-out rate of 15%, and autoregressive covariance structure, with correlation between sequential assessments set at 0.45. Autoregressive covariance structures assume points closer together in time are more correlated than points further in time, which is more plausible compared to the equal correlation between all pair of assessments regardless of time separation assumed by the compound symmetry design. *When multiple analyses are conducted for a given hypothesis, Type I error rates will be controlled*

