*by a Westfall-Young procedure, we would include an alpha level of .04 for Hypothesis 1a, .03 for Hypothesis 1b and 2a, and .05 for Hypothesis 2b.* We estimate that with the proposed sample size of 192 (15% drop-out) patients (96 for each of the two groups), the study will have minimum power of 80% to yield a statistically significant result for a medium effect size. Hedker et al. defined medium effect size in this model as a between-group difference increasing linearly from 0 at baseline to .5 SD units at the last time point. Hypothesis 2b is a cross-sectional hypothesis using data collected only in the week 14 of the study. The proposed sample size will provided us with a minimum power of 90% to detect a medium to large effect size. The former and foundational Behavioral Activation for PTSD study by [name] and [name] yielded the following rates which also informed our proposed sample size determination: 192 screened, 81 enrolled, 10 dropped (12.3% dropout rate), 101 screen failures.

**Outcome analyses:** Data analyses will proceed in stages. Descriptive statistics and exploratory graphing such as frequencies, means, standard deviations, stem and leaf diagrams, and scatterplots will be used to assess normality of data in terms of presence of skew and/or outliers. Continuous outcome data will be transformed if necessary using an appropriate transformation such as the log transform for skewed long tailed data. Prior experience with this kind of data leads us to expect that for all variables, the distributions will be skewed and the variances not homogeneous. Similarly, potential covariates will be summarized with descriptive statistics and graphs to determine the most appropriate way to treat these variables (e.g., continuous, categorical, or interval representation). For outcome measures acquired at baseline, 7, and 14 weeks, the analytical approach will address the nature of the outcome, as well as accommodate the within

individual variability due to the repeated assessments. Results from will be inspected for bias due to drop-outs or missing data.

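### The saturated treatment-by-time model is valid, but it names no test contrast and leaves baseline means free; a 1-df week-14 test that uses baseline is at least as precise

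*Combined protocol and SAP*

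**What the plan says.** All references are to section 5.6 unless noted.

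- **Factors for Hypotheses 1a and 1b:** "Independent variables: Treatment group (2 levels, CABA and TAU), & Time (3 levels, Weeks 0, 7, and 14". Week 0 is thus a response level, not a covariate.
- **Inference:** "A fully saturated treatment by time model will be utilized for inference". No week, contrast or degrees of freedom is attached to the test. Hypothesis 2a is to be analysed in a similar way.
- **Power text:** "With random assignment to groups, there should be no group differences in baseline values, and slopes differences reflect treatment effects", and the design is described as one "where the slope is the dependent measure". The correlation is autoregressive, "with correlation between sequential assessments set at 0.45". Sidedness is listed as a needed assumption ("nature of the hypothesis (one- or two-sided") but never given.
- **Alphas:** "we would include an alpha level of .04 for Hypothesis 1a, .03 for Hypothesis 1b and 2a, and .05 for Hypothesis 2b", tied to a Westfall-Young procedure where a hypothesis has several analyses.
- **Outcome analyses:** the plan expects that "for all variables, the distributions will be skewed and the variances not homogeneous".
- **Adjustment:** comparisons may be adjusted for participant characteristics, but the baseline outcome is not prespecified as a covariate and the baseline means are not constrained.
- **Visits (Table 3, section 5.5):** PCL-5, NSI, BDI-II and SLS are taken at weeks 0, 7 and 14. CAPS-V and the neuropsychological battery are taken at weeks 0 and 14 only.

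**The concern.** The plan itself says that randomisation should equalise the baseline means, yet the inference model estimates them separately by arm and so does not use that fact. With no contrast named, the slope wording is the only pointer. With visits at weeks 0, 7 and 14, the linear contrast is week 14 minus week 0.

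A change contrast carries the full baseline noise, and that is costly when the week 0-14 correlation is low. Under the plan's autoregressive assumption it is .45² = .2025.

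Two things are at stake. One is precision that the trial could have from data it already collects. The other is that the choice among a slope, a change, a week-14 difference and a 2-df interaction stays open after the data are seen.

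**Working it through.** **Inputs.** 96 per arm less 15% dropout gives 81.6. The effect is 0.5 SD at the last visit, and the adjacent-visit correlation is .45. Alpha is .04 (1a) and .03 (1b, 2a). Table 1 (Preliminary Studies) gives the pre and post SDs. My assumptions: two-sided tests, each alpha applied to a single test, 0.5 SD in week-14 SD units, and a normal approximation.

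**Variance per participant** (s0, s1 = SD at weeks 0 and 14; r = their correlation):
- change: s0² + s1² − 2·r·s0·s1
- plain week-14 difference: s1²
- week-14 difference using baseline: s1²(1 − r²)

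Change minus the last is (s0 − r·s1)². Plain minus the last is r²·s1². Neither can be negative, which is the large-sample result. The gain over change is zero at r = s0/s1.

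**The plan's own figure.** The plan states at least 80% power. With equal SDs and r = .2025, the change variance is 2(1 − .2025) = 1.595, and a GLS slope over the three visits has the same variance. SE = √(2 × 1.595/81.6) = .198, so 0.5/SE = 2.529. Power is 64% at .03 and 68% at .04, which does not reproduce 80%. If .45 is instead taken as the week 0-14 correlation, the variance is 1.100 and power is 81% and 84%, which does.

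**Equal SDs**

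| | r = .2025 | r = .45 |
|---|---|---|
| Change variance | 1.595 | 1.100 |
| Plain week-14 variance | 1.000 | 1.000 |
| Week-14 variance using baseline | .959 | .7975 |
| Cut against change | 40% | 27.5% |
| Cut against plain week 14 | 4% | 20% |
| Power at .03 / .04, change | 64 / 68% | 81 / 84% |
| Power at .03 / .04, plain week 14 | 85 / 87% | 85 / 87% |
| Power at .03 / .04, using baseline | 86 / 89% | 92 / 94% |

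Share of the gain due to the choice of contrast alone: (1.595 − 1)/(1.595 − .959) = 94% at r = .2025, and (1.100 − 1)/(1.100 − .7975) = 33% at r = .45.

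**Table 1 SDs, pooled over arms (root mean square)**

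| | s0 / s1 | Cut at r = .2025 | Cut at r = .45 | Zero gain at r |
|---|---|---|---|---|
| CAPS | 15.3 / 25.9 | 13.6% | 2.4% | .59 |
| PCL | 8.2 / 13.0 | 16.0% | 3.9% | .63 |
| BDI-II | 7.6 / 10.6 | 21.7% | 8.3% | .72 |

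Example, CAPS at r = .2025, with unrounded SDs: change 741.8, using baseline 641.1, and 1 − 641.1/741.8 = 13.6%. Beyond the zero point the gain rises again slowly; at r = .7 it is 2.3% for CAPS and 0.9% for PCL. With these SDs and r = .2025, the change contrast already has 84% (CAPS) and 83% (PCL) power at .04, and 76% (BDI-II) at .03.

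**Dropouts' baselines kept in the fit.** With 15% missing at week 14, the equal-SD cut is 24-36% rather than 27.5-40%.

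**Degrees of freedom (three-visit outcomes only).** Equal SDs, autoregressive .45, effects .25 and .5 at weeks 7 and 14. The 2-df interaction has 53% and 58% power at .03 and .04 with free baselines, and 79.5% and 82.6% with a common baseline. The 1-df week-14 test using baseline has 86% and 89%.

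**The case against.** **The comparator is inferred.** No section says that the primary test is week 14 minus week 0, and the saturated model can deliver the plain week-14 difference as it stands. Against that, using baseline saves 4-20% with equal SDs. At r = .2025 nearly all of the 40% is contrast choice. This stands, and it is why naming the contrast comes first.

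**Equal SDs do not match the only SD data in the protocol.** Table 1 shows SDs rising from before to after treatment. Backing an average correlation out of its F and eta-squared values gives roughly .64 (PCL) and .75 (CAPS), assuming about 45 completers and one common correlation. The gain there is about 0-5.5%. This stands for CAPS and PCL. Table 1 does not cover NSI, SLS or the neuropsychological tests, and it comes from an earlier trial with older CAPS and PCL versions.

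**A reader might infer a guaranteed power level whatever the correlation and SD ratio.** The documents do not support that. The plan does not say which SD its effect is measured in. If it is the baseline SD, power using baseline at .04 with Table 1 SDs and r = .2025 is about 45% (CAPS) and 50% (PCL). Multiplicity adjustment also lowers power: at a Bonferroni bound for four 1b outcomes (.03/4 = .0075), even the plain week-14 test has 69.8%. Westfall-Young falls between that and the unadjusted 85%.

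**A reader might also infer that the change contrast misses 80% at every alpha in the plan.** It does not. One-sided .05 gives 81.2% with equal SDs and r = .2025, although that alpha belongs to 2b.

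**Conclusion.** The point holds as a modest improvement to consider. The planned model is valid and unbiased; reading it as an error, or as proof that the trial is underpowered, goes beyond the documents. The power shortfall appears with equal SDs and a literal r = .2025. It disappears for CAPS and PCL at .04 with Table 1 SDs and the week-14 SD unit.

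What is established is that the contrast is unnamed, the baseline means are free, and a 1-df week-14 test using baseline costs nothing in large-sample precision under any correlation. Against the implied change contrast, variance falls 0-16% for CAPS and PCL (Table 1 SDs, r from .2025 to .7) and 27.5-40% with equal SDs. With equal SDs and r = .2025, power rises from 68% to 89% at .04 and from 64% to 86% at .03. Those power figures rest on two-sided tests, 81.6 per arm, the week-14 SD unit and no Westfall-Young adjustment. No general power floor is claimed.

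The degrees-of-freedom point applies only to PCL-5, NSI, BDI-II and SLS. CAPS-V and the neuropsychological tests already have a 1-df interaction.

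**What to change.** For the 1a, 1b and 2a outcomes, prespecify the 1-df CABA minus TAU difference at week 14, averaged over sites.

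- **Model:** PROC MIXED with one baseline mean per site shared by both arms (treatment coded 0 at week 0), unstructured covariance, and the planned site and treatment-by-site terms.
- **Alternative:** use post-baseline visits as the response, with baseline and baseline-by-time as covariates. Use this version if a generalised model is chosen.
- **Transformation:** apply any transformation alike at all visits.
- **Analysis set:** fit the shared-baseline model to every randomised participant with a baseline value, dropping the requirement of a post-baseline visit. Section 5.5 also excludes participants whose missed session content cannot be made up. That rule can remove CABA participants only, so it can undo the baseline equality that the constraint relies on. Confine it to a sensitivity analysis.
- **Assumptions to state:** sidedness, and which SD the 0.5 refers to.

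The cost is a short SAP revision, modest recoding, a wider analysis set and the loss of AIC covariance selection for these tests. No new data are needed. Make the change before any unblinded analysis.
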